6.5 ONGOING DIABETES MANAGEMENT

All study participants will have a treating endocrinologist who is primarily responsible for their diabetes care. In general, the expectation is that all participants will receive at least three injections of insulin daily, including short- and long-acting insulin preparations, or will utilize continuous subcutaneous insulin infusion (CSII, insulin pump). As part of diabetes monitoring during the subjects' participation, we will encourage participants to check glucose levels at least four times daily if using blood glucose monitor and if not already using a CGM. **At the time of visits the study team** will suggest changes that they believe would improve the glucose control, if necessary. Letters summarizing the study visit will also be sent to the endocrinologist after parental agreement.

In addition, insulin use, hypoglycemic events, and any episodes of ketoacidosis will be captured at each visit on the appropriate CRFs.

Participants will be requested to record the amount of insulin they have used during the 3-day period immediately preceding each study visit. Insulin use logs will be provided to participants at each study visit and collected at the next visit. These logs will serve as the source documents.

6.6 BANKED SPECIMENS

Serum and plasma will also be banked and stored at Indiana University for other type1 diabetes related assays and for potential future use by other investigators. Participants will have the option to not have samples stored on the informed consent documents.

7.0 REPORTING OF ADVERSE EVENTS OR UNANTICIPATED PROBLEMS INVOLVING RISK TO PARTICIPANTS OR OTHERS

7.1 UNANTICIPATED PROBLEMS

In the unlikely event of an acute emergency with a subject, all procedures will be performed in a hospital setting by trained personnel.

In the event of physical injury resulting from the participation in this research, necessary medical treatment will be provided and billed as part of their medical expenses. Costs not covered by health care insurer will be the subject's responsibility. Also, it is the subject's responsibility to determine the extent of health care coverage. There is no program in place for other monetary compensation for such injuries. However, the subject will not give up any legal rights or benefits to which he/she is otherwise entitled. If any severe adverse events occur while not at a medical facility, the subject will be responsible for seeking medical care and for the expenses associated with any care received.

7.2 DATA SAFETY MONITORING

The data safety monitoring plan involves [name], MD, a pediatric endocrinologist, to review this study for data for quality, rate of subject recruitment, adverse events, procedures for protecting patient privacy, and any protocol deviations every 6 months following the first subject enrolled. If the review concludes that there are significant safety concerns or quality of the data is unsatisfactory, no further enrollment will occur until these issues have been addressed and any changes to the study approved by the IUPUI IRB.

7.3 ADVERSE EVENTS

An adverse event is defined as any unintended or abnormal clinical observation that is not of benefit to the patient. Either the condition was not present prior to exposure to study supplement, or it has worsened in intensity or frequency following exposure to the study supplement. Adverse events will be graded according to the National Cancer Institute (NCI) Common Terminology Criteria v5.0.

https://ctep.cancer.gov/protocolDevelopment/electronic_applications/docs/CTCAE_v5_Quick_Reference_5x7.pdf

Any suspected or confirmed toxicity should be reported immediately (within 24 hours) to the principal investigator.

Hypoglycemic and hyperglycemic events that are seen as part of daily diabetes management will not be considered adverse events unless they result in hospitalization

Principal investigators (PI) will report to the IRB as soon as possible, but in all cases within 5 working days from notification any event that appears on the List of Events that Require Prompt Reporting to the IUPUI IRB.

List of Events that Require Prompt Reporting to the IUPUI IRB: Any of the following:

- Event (including adverse events, injuries, side effects during the research study), which in the opinion of the PI
 - caused harm to one or more subjects or others, or placed one or more subjects or others at increased risk of harm; AND
 - was unexpected; AND
 - was related to the research procedures

Note: After the study is closed with the IRB, these events will only be reported if they are profound, or they demonstrate long-term risks that would necessitate notifying subjects.

- Protocol deviation/violation (as defined under this policy)
- Change to the protocol taken without prior IRB review to eliminate apparent immediate hazard to a research subject (e.g., purposeful and for subject safety)
- Complaint of a subject that indicates unexpected risks, or complaint that cannot be resolved by the research team
- Interim findings and safety monitoring reports that indicate an unexpected change to the risks or potential benefits of the research, in terms of severity or frequency
- Publication in the literature that indicates an unexpected change to the risks or potential benefits of the research
- Change in FDA labeling or withdrawal from marketing of the supplement used in this research study
- Noncompliance (as defined in this policy)

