6.1 STUDY DESIGN

6.2 RANDOM ASSIGNMENT

Subjects will be randomly assigned (6 in each arm) to either HAMS-AB plus a recommended diabetic diet or control diabetic diet alone [49, 50] for the first 4 week of treatment period. After a suitable washout period during which participants do not need to follow the recommended diet or use the supplement, subjects will continue for 4 weeks after a cross-over. All participants will be expected to follow the guidelines for a healthy diabetic diet during the study period, except for during the 4-week washout period.

A computer-based randomization plan will be prepared by the principal investigator. The document will be kept by the study team for use. As a subject is screened and qualifies, he/she will be assigned in order of screening date on the computer-generated document. One master list will be maintained in a confidential central shared folder for use. Subjects will be replaced on an ongoing list if they drop out.

Participants will be instructed to consume HAMS-AB with food, such as apple sauce or oatmeal, in two divided doses at breakfast and dinner at a total daily dose to be calculated as has been previously described for children: 10g plus 1g per year of age daily [44]. The prebiotic will be dispensed by the Investigational Drug Services (IDS) at Indiana University.

HAMS-AB will be in the form of acetylated and butyrylated **HYLON® VII** corn starch.

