6.4 STUDY VISITS

Visit 1 – Screening

This visit will be at the hospital or research center. It will last approximately 1-2 hours and will include:

- Obtain informed consent/assent documents and determine inclusion and exclusion criteria
- Measurement of height and weight to determine BMI percentile eligibility and physical exam including pubertal staging
- Obtaining Vital signs (heart rate, temperature, blood pressure, and respiratory rate)
- Obtaining medical history
- Dietary assessment by verbal recall
- Obtaining blood sample (approximately 1.5 tablespoon) – Random non-fasting c-peptide, pancreatic autoantibodies if not previously done to confirm T1D diagnosis
- For female adolescents: urine will be collected for a pregnancytest
- Subject to sample prebiotic for palatability to ensure compliance

Visit 2 – Baseline-Intervention

This visit will be at the hospital or research center. It will last approximately 1-2 hours and will include:

- Measurement of weight and bedside nurse assessment such as general appearance, respiratory and cardiac assessment.
- Obtain vital signs (heart rate, temperature, blood pressure, and respiratory rate)
- Collecting a diet history (diary or questionnaire)
- Collecting Adverse Events (if applicable)
- Obtaining medical history and insulin use

Obtaining blood samples (approximately 2 tablespoons) – HbA1c, Serum biomarkers of beta cell stress and death (PI:C and INS DNA), other T1D testing, and serum and plasma for storage.

- Some of the blood will be stored for future T1D research use

- CGM placement and training for participants not currently using one.
- For female adolescents: urine will be collected for a pregnancytest
- Collecting stool samples prior to or the morning of the visit (a stool collection kit will be shipped to the participants once eligibility is confirmed)
- Study Randomization to either supplement or standard of care diabetes management and a diabetic diet.
– Supplement (HAMS-AB) will be provided and will be taken by mouth twice daily with food such as apple sauce or oatmeal as described in Section 6.2. Instructions will be provided for recommendations on a healthy diabetic diet.
- A new stool collection kit will be provided for the next visit

Visit 3 - Washout

This visit will be at the hospital or research center. It will last approximately 2-4 hours and will include:

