- Measurement of weight, assessment of CGM insertion sites, as well as bedside nurse assessment such as general appearance, respiratory and cardiac assessment.
- Obtaining Vital signs (heart rate, temperature, blood pressure, and respiratory rate)
- Collecting a diet history (diary or questionnaire)
- Collecting Adverse Events (if applicable)
- Obtaining medical history and insulin use
- CGM download
- For female adolescents: urine will be collected for a pregnancytest
- Collecting stool samples prior to or the morning of the visit
- Obtaining fasting blood sample (approximately 5 tablespoons) – Serum biomarkers of beta cell stress and death (PI:C and INS DNA), other T1D testing, and serum and plasma for storage and MMTT

- samples (see below), and serum and plasma for storage
 - Some of the blood will be stored for future T1D research use
- Completion of a mixed meal tolerance test (MMTT). See below.
- After completion of this visit, participants will be instructed to follow a regular diet with no supplement intake for the following 4 weeks and to follow standard diabetes care as instructed by their diabetes provider.
- A new stool collection kit will be provided for the next visit

Preparing for an MMTT

- Subjects will be asked to fast except for water for at least 10 hours prior to visit.
- Subjects will be asked to limit strenuous activity for at least 10 hours prior to visit.
- Subjects will be asked to consume at least 150 g of carbohydrates each day for 3 days.
- If subject experiences hypoglycemia, morning of the visit, subjects will be instructed to treat low blood sugar and to reschedule MMTT procedure.

MMTT Visit procedures

Blood glucose will be tested and the MMTT started if blood glucose <200 by 10:00am. Long-acting insulin may be taken per routine, but short acting insulin must not have been given within 2 hours of MMTT.

An IV catheter will be placed in the arm by trained nurses for blood drawing purposes. Blood will be drawn 10 minutes prior to drinking Boost, just prior to drinking Boost, 15, 30-, 60-, 90-, and 120-minute post Boost consumption. High Protein Boost will be measured to a dose of 6ml/kg body weight (maximum dose 360ml). Total volume of blood will be approximately (5 tablespoons) not to exceed 5ml/kg/day.

Visit 4 Crossover-Intervention

This visit will be at the hospital or research center. It will last approximately 1-2 hours and will include:

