8.0 STATISTICAL CONSIDERATIONS

A sample size of 12 with a cross over design (i.e., 12 per arm) is considered adequate to estimate effect sizes for efficacy to aid in designing future trials for responses that are normally distributed [52]. Simple comparisons will be performed using chi-square for categorical variables and t-tests for continuous variables. Random attritions and failed screens will be replaced. An intention to treat analysis will not be appropriate given the crossover design. Adverse events will be presented as the proportion of each event seen. This is considered a minimal risk study with low risk for minor adverse events such as mild gastrointestinal symptoms that could be related to increased dietary fiber intake. Our primary outcome is changes in the gut microbiome profile. To determine the diversity and richness of the microbiome, we will calculate a diversity index for both the pre- and post-intervention time points for each recipient. Microbial sequence analysis and statistics will be analyzed using the Quantitative Insights into Microbial Ecology (QIIME) 1.8.0 software as previously described [53].

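### Adverse events are defined from an undefined supplement exposure and not split by condition, so whether a symptom counts can depend on sequence (minor)

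*Combined protocol and SAP*

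**What the plan says.** Section 7.3 opens broadly: "An adverse event is defined as any unintended or abnormal clinical observation that is not of benefit to the patient". The next sentence narrows this: "Either the condition was not present prior to exposure to study supplement, or it has worsened in intensity or frequency following exposure". Both halves of that sentence refer to exposure to the supplement, and the term is not defined anywhere.

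The design is a two-sequence crossover. Section 6.2 states: "Subjects will be randomly assigned (6 in each arm) to either HAMS-AB plus a recommended diabetic diet or control diabetic diet alone". Under Sections 3.2 and 6.4 each treatment period lasts 4 weeks, with a 4-week washout between them during which no supplement is taken. The control-first participants are therefore first supplied with HAMS-AB for treatment at Visit 4.

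The supplement is also tasted at screening. The Visit 1 list in Section 6.4 includes: "Subject to sample prebiotic for palatability to ensure compliance". The schedule in Section 6.3 shows this as a separate line from the provision of HAMS-AB.

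The schedule marks adverse event assessment at Visits 2 to 5 and at early termination, in both sequences. A footnote adds questions on stools, gut symptoms, fever and infection.

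On analysis, Section 8.0 (Statistical Considerations) says only: "Adverse events will be presented as the proportion of each event seen". It gives no denominator, period or condition.

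**The concern.** In a parallel-group trial of a supplement, a definition tied to exposure would simply leave out the control arm, and the gap would be obvious. In a crossover it works through sequence. A symptom that begins in the control weeks of a control-first participant was present before dosing. It fails the first half of the qualifier and meets the second only if it worsens on HAMS-AB. The same symptom in the control weeks of a HAMS-AB-first participant begins after dosing, so it counts.

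Section 3.5 expects abdominal discomfort and more frequent bowel movements in more than 20% of those taking HAMS-AB. A reader of the results will want a control-period figure to set beside that. Section 3.5 also lists sensor-site reactions and nausea after the Boost drink. In control-first participants, the first study sensor (for those not already using one) and the Visit 3 meal test both come before any dosing, so such events could go unclassified. Even if every event is classified, a single proportion per event does not show whether the participant was on HAMS-AB, control or washout when it began.

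**Working it through.** **Inputs.** 6 participants per sequence (Section 6.2); 4 weeks per treatment period and 4 weeks of washout (Section 3.2); order HAMS-AB, washout, control or control, washout, HAMS-AB (Sections 3.1 and 6.2). The documents give no background event rate.

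**The plan's own figure.** Section 8.0 counts 12 per arm under the crossover. 6 per sequence × 2 sequences = 12 per condition, which agrees.

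**Planned person-weeks.** Each condition has 12 × 4 = 48: HAMS-AB 48, control 48, washout 48, total 144.

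**Person-weeks in which a new event meets the definition**

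| Condition | Planned | Exposure = dosing | Exposure = Visit 1 sample |
|---|---|---|---|
| HAMS-AB | 48 | 48 | 48 |
| Control | 48 | 6 × 4 = 24 | 48 |
| Washout | 48 | 6 × 4 = 24 | 48 |

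On the dosing reading, 48 of the 96 control and washout person-weeks are excluded (50%). On the sample reading, 0 of 96 are. An event in the excluded weeks that later worsens on HAMS-AB would still count, so the exclusion applies to new events that do not worsen.

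**Dependence on the split.** Section 6.2 adds: "Subjects will be replaced on an ongoing list if they drop out". The final split may therefore not be 6:6. With 12 participants, the excluded share of control and washout time is (number control-first × 8)/(12 × 8). For HAMS-AB-first to control-first splits of 4:8, 6:6 and 8:4 this is 67%, 50% and 33%.

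**What it would do to a control-period proportion.** This is an illustration only. It needs the dosing reading, a by-condition table that Section 8.0 does not plan, and an assumed true control-period risk p.

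- Over 12 participants the expected proportion is 6p/12 = p/2. For p = 5%, 20% and 40% this gives 2.5%, 10% and 20%. These are lower bounds, because events that later worsen would be added.
- Over the 6 exposed participants the expected proportion is 6p/6 = p, unbiased if there is no period or carry-over effect. All 6 are HAMS-AB-first, so every countable new control event comes from the last 4-week period.
- The standard error is √(p(1−p)/n). With n = 6 it is 8.9, 16.3 and 20.0 percentage points; with n = 12 it is 6.3, 11.5 and 14.1.
- With no events, the exact two-sided 95% upper limit is 1 − 0.025^(1/n): 45.9% for n = 6 and 26.5% for n = 12.

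**After the fix.** With one start point common to both sequences, 0 of 96 control and washout person-weeks are excluded and all 144 count.

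**The case against.** The strongest reply is that the dosing reading is not what the text says. Section 7.3 speaks of exposure, and every participant is due to take some of the supplement at Visit 1, before randomisation. Read literally, everyone is exposed before Visit 2 and nothing is lost. The schedule supports this. Adverse events are asked about at Visit 2, when HAMS-AB is first handed out, and again at Visits 3 and 4 in control-first participants. On the dosing reading, none of those reports could be a new adverse event. The opening sentence of Section 7.3 has no exposure limit, and the qualifier may be meant only to set aside pre-existing conditions. Finally, Section 8.0 plans no comparison by condition, so no planned result is biased.

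Most of this stands. The dosing reading is not forced, and the halved control proportion and the standard errors are conditional illustrations, not a predicted bias.

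Two things remain. No section says that the Visit 1 sample is exposure; its stated purpose is palatability, and the schedule lists it apart from provision of HAMS-AB. A counting rule that excludes either 50% or 0% of control and washout time, depending on an undefined word, needs defining. And the absence of any split in Section 8.0 is itself a gap on either reading, because events from three conditions are then not told apart.

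**Conclusion.** The point holds as a minor one. Section 7.3 leaves the start of exposure open. On one of the two available readings, the same symptom counts or not according to sequence. The size is 24 of 48 control and 24 of 48 washout person-weeks on the dosing reading at a 6:6 split, and none on the Visit 1 reading. The missing split by condition in Section 8.0 holds whichever reading is taken.

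A reader might infer more, and the documents do not support it:

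- **That control-period events go unrecorded.** The schedule collects adverse events at every visit from Visit 2 in both sequences.
- **That safety reporting is weakened.** The prompt-reporting list for the IRB begins "Event (including adverse events, injuries, side effects during the research study), which in the opinion of the PI", and its conditions are harm or increased risk, unexpectedness and relation to the research procedures. None requires exposure to the supplement.
- **That the control rate will be halved.** This needs the dosing reading, a denominator of 12 and an unplanned table, all together.
- **That no event in the affected weeks can ever count.** One that worsens on HAMS-AB does.

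Safety is neither an objective nor an endpoint in Sections 2.0 and 3.4, and the planned adverse event figures are descriptive.

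**What to change.** In Section 7.3, define an adverse event as any untoward event with onset or worsening between the Visit 1 sample and the last visit, regardless of supplement exposure. Starting at the Visit 1 sample, rather than at randomisation, keeps reactions to that sample within the definition. List events that arise before treatment starts at Visit 2 separately.

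In Section 8.0 (Statistical Considerations), present the number and proportion of participants with each event by condition at onset (HAMS-AB, control, washout). The denominator should be all participants who entered that period.

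The cost is minor wording in two sections and one descriptive table. No new data are needed: the Visit 2 questions cover the time since screening, and Visits 3, 4 and 5 each close one period.

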AIM 1: Determine the effect of HAMS-AB on the gut microbiome profile and SCFA production in children with recently diagnosed T1D. We *hypothesize* that HAMS-AB consumption will shift the gut microbiome to microbial populations that are capable of HAMS-AB fermentation and increase SCFA production. Twelve youths (11-17 years old) will consume HAMS-AB or follow the standard of care recommended diabetic diet daily for [49,50] 4 weeks and then cross over after a 4-week washout period. DNA will be extracted from fecal samples obtained followed by 16S RNA sequencing for gut microbial community analysis at baseline and at each visit during the study period [32, 33]. SCFAs will be analyzed using standard methods [36, 37].

AIM 2: Determine the effect of HAMS-AB on glycemia and β -cell function and health. We *hypothesize* that the prebiotic HAMS-AB will improve overall glycemia including reducing glycemic variability in recently diagnosed persons with T1D. We will compare glycemic/ β -cell measures pre/post intervention with HAMS-AB and between the intervention and control groups. We will measure glycemia using HbA1c, average glucose and glucose variability using continuous glucose monitoring (CGM) [38-40]. We expect to see an improvement in glycemia in response to HAMS-AB intake. We will assess β -cell function using mixed meal tolerance (MMTT)-derived C-peptide measures. We *expect* that measures of β -cell stress/death will show improvement following the use of HAMS-AB. We will determine β -cell stress using proinsulin/C-peptide (PI:C) ratios [41]. We will assess β -cell death by differential methylation of proinsulin (INS) DNA [42].

Upon successful completion of this pilot study, we expect to assess the effect of prebiotic administration on the gut microbiome profile, SCFA production, glycemia and β -cell function in humans with T1D. The knowledge generated by the proposed research will provide critical experimental information needed to substantiate a fully powered study.

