13 PRECLINICAL AND CLINICAL EXPERIENCE

HAMS is a prebiotic that is a well-tolerated source of dietary fiber with selective fermentation properties. In T1D mouse studies [21], feeding HAMS that has been acetylated and butyrylated (HAMSA and HAMSB) shifts the gut microbiome profile towards fermenters, resulting in increased acetate and butyrate production and lower rates of progression to T1D, Figure 1.

In a human study assessing the effects of 2 levels of intake of HAMS [15 or 30 g/d (double-blind)] compared to control starch intake (0 HAMS) for 4-wk periods separated by 3-wk washouts on insulin sensitivity (SI) in participants with increased waist circumference, it appeared that the consumption of 15–30 g/d of HAMS improved insulin sensitivity significantly in men, Figure 2 [27].

In another human randomized, double-blind, controlled study [28] in healthy adults who consumed either a high fiber scone containing a novel chemically modified high amylose maize starch or a low fiber control scone without the maize starch, the consumption of the high fiber scone significantly reduced postprandial glucose and insulin incremental areas under the curves (43–45% reduction, 35–40% reduction, respectively) and postprandial glucose and insulin maximum concentrations (8–10% and 22% reduction, respectively), Figure 3. Of note, ingestion of the high fiber scone consumption was not associated with increased gastrointestinal side effects compared with the control scone.

Figure1: Incidence of T1D in female NOD mice fed the NP diet ($n = 25$ mice), HAMS diet ($n = 17$ mice), HAMSA diet ($n = 11$ mice), HAMSB diet ($n = 12$ mice) or combined (HAMSA plus HAMSB) diet ($n = 11$ mice) for 10 weeks (HAMSA plus HAMSB; orange arrows) or 5 weeks (all other diets; blue arrows), starting at 5 weeks of age. NS (NP vs HAMS, HAMSB vs HAMS, HAMSP vs HAMS, and HAMSP vs NP); $*P = 0.0482$ (HAMSB vs NP), $\#P = 0.0490$ (HAMSA vs HAMS), $**P = 0.0069$ (HAMSA vs NP), $\#\#P = 0.0025$ (HAMSA+HAMSB vs HAMS) and $***P = 0.0008$ (HAMSA+HAMSB vs NP) (Mantel-Cox log-rank test) [22].

Conventional, non-purified (NP), High-amylose maize starch (HAMS) that has been acetylated (HAMSA) or butyrylated (HAMSB), non-significant (NS).

[figure not shown]

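### Section 7.3 takes glucose events of daily diabetes management out of the adverse events unless hospitalized, so more frequent lows on HAMS-AB could reach no planned safety summary

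*Combined protocol and SAP*

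**What the plan says.** Section 7.3 defines an adverse event broadly. A condition already present before exposure qualifies if "it has worsened in intensity or frequency following exposure to the study supplement". The same section then makes an exception: "Hypoglycemic and hyperglycemic events that are seen as part of daily diabetes management will not be considered adverse events unless they result in hospitalization". The events that belong to daily management are not defined.

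Three later steps are worded in terms of adverse events:

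- **Grading (7.3):** "Adverse events will be graded according to the National Cancer Institute (NCI) Common Terminology Criteria v5.0".
- **Results (8.0, Statistical Considerations):** "Adverse events will be presented as the proportion of each event seen".
- **Safety review (7.2):** one physician reviews data quality, "rate of subject recruitment, adverse events, procedures for protecting patient privacy, and any protocol deviations every 6 months following the first subject enrolled".

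Separately, Section 6.5 says that "insulin use, hypoglycemic events, and any episodes of ketoacidosis will be captured at each visit on the appropriate CRFs". No section says how those CRF entries will be summarized, compared between conditions or passed to the safety reviewer. The glycemic measures named in Aim 2 are HbA1c, mean glucose and glucose variability; the last two come from CGM. None of them measures low glucose.

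**The concern.** Participants are insulin-treated youths, and the trial hopes the supplement will improve glycemia. If HAMS-AB lowers glucose, some of the fall may come as more frequent low glucose. Under the plan, the fall in the mean would be reported as benefit. The extra lows would sit on CRFs with no planned table and, if handled under the exception, would be neither graded nor counted as adverse events.

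The pilot is meant to inform a fully powered study, and the Study Benefits section looks ahead to whether treatment can preserve beta cells safely. A clean adverse event table would be read as support for that, although part of the relevant experience had been set aside by definition.

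**Working it through.** The documents give no hypoglycemia rate and no figure on this point, so there is nothing to reproduce. The check sets the sections side by side and then sizes the exposure.

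**1. Where each kind of event goes**

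| Event | On a CRF (6.5)? | Adverse event (7.3)? | Graded, summarized, in the reviewer's adverse events? |
|---|---|---|---|
| Routine low, not hospitalized | Yes | No, under the exception | No |
| Lows more frequent after starting HAMS-AB, not hospitalized | Yes | Yes by the definition, no by the exception | Contradictory |
| Severe low or ketoacidosis treated outside hospital | Yes | Unclear: turns on the undefined qualifier | Unclear |
| High glucose without ketoacidosis, not hospitalized | Not named | No, if part of daily management | No |
| Any glucose event leading to hospitalization | Yes for lows and ketoacidosis | Yes | Yes |

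The second row is an internal contradiction. The third is an ambiguity. The first is the intended effect of the exception, and it is reasonable for a single mild event. It becomes a problem only because nothing else counts such events by condition.

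**2. Whether another planned output fills the gap**

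- A lower mean glucose is read as benefit.
- Variability mixes highs and lows. More lows push it up and fewer highs pull it down, so it cannot isolate lows.
- HbA1c is an average, and the schedule takes it only at Visits 2 and 5.
- The visit safety questions ask about well-being and adverse events. The specific topics listed are stool, gastrointestinal symptoms, fever and infection.
- The supplement risks in the Study Risks section are abdominal and bowel symptoms only.

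**3. Why low glucose is a plausible effect**

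Section 4.4 attributes the action of HAMS to an altered microbiome with better glycemia and insulin sensitivity. Section 6.5 expects at least three insulin injections daily or a pump. The dose formula in 6.2 gives 10 + 11 = 21 to 10 + 17 = 27 g/d across the eligible ages. That lies within the 15–30 g/d at which, in a cited study, HAMS "improved insulin sensitivity significantly in men". The step from there to more lows in this population is an inference; the documents do not state it.

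**4. Exposure**

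Inputs: 12 participants (8.0) and 28 days per condition (schedule of events).

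- Per condition: 12 × 28 = 336 person-days, or 48 person-weeks.
- In years: 336 / 365.25 = 0.92 person-years on HAMS-AB, and the same on control.
- For even one expected hospitalized glucose event per condition, the rate would have to be 1 / 0.92 = 1.09 per person-year.

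These are nominal values for 12 completers; replaced participants would add a little. An adverse event table that admits glucose events only through hospitalization can therefore say little about low glucose.

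**5. Whether the data exist**

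Hypoglycemia and ketoacidosis are captured at each visit. CGM is downloaded at Visits 3 and 5, the ends of the two intervention periods. The gap is in definition, analysis and routing, not in collection.

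**The case against.** Routine glucose excursions are part of living with type 1 diabetes, and keeping them out of the adverse events is sensible. The exception covers only events of daily management, and the data are recorded anyway. Section 7.3 has other routes: suspected toxicity goes to the principal investigator within 24 hours, and the IRB list covers any event judged harmful, unexpected and related, not only adverse events. Section 5.3 provides for early termination after a medically important event. The reviewer's remit includes data quality, and enrollment can be paused for significant safety concerns. Safety is not a listed objective or endpoint.

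Much of this stands, and it rules out four stronger readings that a reader might infer:

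- **That every non-hospitalized glucose event is excluded.** The qualifier limits the exception. A seizure, or ketoacidosis treated in an emergency department, is ambiguous rather than plainly excluded.
- **That the trial's own mechanism predicts this harm.** The insulin-sensitivity study enrolled people with increased waist circumference (11 men, 22 women) and reported its significant result in men. The postprandial study used another modified starch in healthy adults. Neither tested HAMS-AB in insulin-treated youths, and the mechanism gives no reason to expect high glucose.
- **That the safety reviewer would not see these events.** Nothing withholds the CRFs; the plan simply does not say they are sent.
- **That a single severe event would be a signal.** The documents give no background rate against which to judge it.

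The other routes do not close the gap. Each depends on case-by-case judgement, and a low in someone taking insulin is easily judged expected. None compares HAMS-AB with control, which is what would show a rise in frequency.

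**Conclusion.** The point holds in this limited form. Section 7.3 contradicts itself on glucose events that become more frequent or intense after exposure, and it leaves the status of severe events treated outside hospital unclear. Because 7.2, 7.3 and 8.0 refer only to adverse events, the hypoglycemia and ketoacidosis CRFs in 6.5 lead to no planned summary or review. A rise in lows on HAMS-AB could therefore pass as improved glycemia.

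That HAMS-AB might cause more lows is inferred from the mechanism and the insulin background. No event count is offered, since the documents give no rate. With about 0.92 person-years per condition, the added information would be descriptive and could not establish or exclude a difference. The contradiction and the missing routing do not depend on the inference and should be corrected in any case.

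**What to change.** Reconcile Sections 6.5, 7.2, 7.3 and 8.0 (Statistical Considerations):

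- **7.3:** Limit the exception to routine mild excursions and say what that means. Record and grade severe hypoglycemia, by a definition the sponsor states, and any ketoacidosis as adverse events whether or not the participant is hospitalized. State how the exception fits with the worsening clause in the definition.
- **6.5:** State that the CRF covers the interval since the previous visit, so that each event can be assigned to HAMS-AB, control or washout.
- **8.0:** Add a descriptive table by condition (HAMS-AB, control, washout) of hypoglycemia and ketoacidosis from the CRFs, giving events, participants affected and days observed. For the two intervention periods, add CGM time in low glucose, with the threshold stated in advance, from data already downloaded.
- **7.2:** Name this table among the items sent to the safety reviewer.

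The cost is protocol wording, a few more events to grade and report, and one extra table. No new data collection is needed, and no treatment rule changes.
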